Bazin et al. demonstrated that the addition of opioids to a mixture of bupivacaine and lignocaine in brachial plexus block doubles the duration of postoperative pain relief. It prolonged the median duration of analgesia after internal fixation of upper extremity fractures from 11.5 to 21 hours.

Sternlo & Hägerdal. found that addition of morphine to 0.5% bupivacaine was not associated with prolongation of intercostal nerve block.

Racz et al. showed that analgesia duration with intramuscular (IM) morphine was indistinguishable from morphine mixed with local anaesthetic after hand and forearm surgery with mixed lidocaine/bupivacaine axillary blocks.

Keskinbora & Aydinli examined the use of bupivacaine versus bupivacaine plus morphine administered via a popliteal catheter for patients with chronic lower extremity pain. The study included a short-term single bolus treatment phase where morphine was noted to prolong analgesia by approximately three hours compared to bupivacaine alone. However, the morphine group experienced significantly greater side effects (nausea and somnolence). More than twice as many patients preferred treatment with bupivacaine alone, even though they required more rescue analgesia.

Mays & Lipman concluded that perineural morphine provided statistically longer lasting pain relief than did either intramuscular morphine or perineural bupivacaine.

Atef et. al, concluded that 2mg of morphine added as an adjuvant to the local anaesthetic during TAP block significantly reduced postoperative pain intensity after inguinal herniorrhaphy.

OBJECTIVES

Primary Objective

- To assess the duration and quality of postoperative analgesic effect of morphine as an adjunct to ropivacaine in a single shot USG guided FICB in patients undergoing ORIF for fracture femur under spinal anaesthesia.

Secondary Objectives

- To compare the requirement of post-operative rescue analgesics following a single shot USG guided FICB with ropivacaine alone and ropivacaine with morphine in patients undergoing ORIF for fracture femur under spinal anaesthesia.
- To compare postoperative sedation score using modified Ramsay Sedation Scale between two groups.
- To compare the postoperative pain scores at 0, 4, 6, 12, 24 h between two groups and use of rescue analgesics.
- To compare the haemodynamics postoperatively between two groups.

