- To compare the occurrence of any postoperative complications (bradycardia, hypotension, PONV, respiratory depression) between two groups.

RESEARCH HYPOTHESIS (Null Hypothesis)

Morphine added to ropivacaine in USG guided FICB does not prolong the duration of analgesia and minimize the requirement of postoperative rescue analgesics following femoral fracture surgeries.

MATERIAL AND METHODS

a. Type of study design:

This is a prospective randomized double blind clinical trial.

It will include patients of American Society of Anaesthesiologists physical status (ASA PS) I and II, scheduled for ORIF for proximal femur fractures divided in two equal groups.

b. Population/Participants:

- **Group A** - Ropivacaine 0.375% 20ml with NS 2ml for FICB
- **Group B** - Ropivacaine 0.375% 20ml with morphine (1mg/ml) 2ml for FICB

c. Population/Participant's selection criteria

I. Inclusion criteria:

All patients undergoing elective femur surgery under spinal anaesthesia

- Age group (18-65 years)
- ASA physical status I and II

II. Exclusion criteria:

All patients with

- Not willing to participate in the study
- Other painful co-morbidities (neuropathies)
- Allergy or any contraindication to study medication
- Psychiatric disorder
- Coagulopathy
- Infection at the site of the block
- Use of other modes of anaesthesia or analgesia besides spinal anaesthesia.

d. Setting: Department of Anaesthesiology and Critical Care, BPKIHS

e. Probable Study period: One Year

f. Ethical Clearance:

Approval of this study will be obtained from the BPKIHS Institutional Review Committee and informed written consent for the procedure will be obtained from all the eligible patients. Every patient will have the right to withdraw from the study at any time.

g. Conflict of Interest: No conflict of interest

h. Sampling Technique: Via a computer generated random number sequence

i. Method of Randomization and blinding

Based on the computer generated random number table, patients will be assigned to either Group A or Group B.

Sequentially numbered white envelopes will be used with study medication mentioned inside. The investigator observing and recording the outcome will be kept unaware regarding the medication group. At the same time subjects will be unaware of the nature of the drug used. The group allocation will be revealed only after analysis of the data.

METHODS (*INTERVENTION / PROCEDURE*):

a. Instruments and drugs

Equipment needed includes the following:

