In the operating table patient will be properly positioned for spinal anaesthesia. Spinal anaesthesia will be administered in sitting position using bupivacaine (hyperbaric) 0.5% (2.5 - 3 ml). The level of sensory block obtained will be checked by using sterile needle. Motor block will be assessed by grading the motor power of the muscles (0 to 5). During intraoperative period all the patients' ECG, HR, SpO₂ and NIBP will be monitored as per the institute's routine protocol. After the completion of surgery and application dressing on the surgical wound the patient will be positioned supine. The skin will be disinfected and the transducer will be positioned to identify the femoral artery and the iliopsoas muscle and fascia iliaca. The transducer will be moved laterally until the sartorius muscle is identified. After a skin wheal is made, the needle will be inserted in-plane. As the needle eventually pierces through the fascia, pop will be felt and the fascia will be seen to "snap" back on the ultrasound image. After negative aspiration, 1 to 2 ml of the drug will be injected to confirm the proper injection plane between the fascia and the iliopsoas muscle. If local anaesthetic spread occurs above the fascia or within the substance of the muscle itself, additional needle repositions and injections will be made. The drug will be injected in aliquots of 5ml alternating with aspiration. The success of the block will be predicted by documenting the spread of the local anaesthetic toward the femoral nerve medially and underneath the sartorius muscle laterally. This time point will be considered as zero hour for our study.

Experienced anaesthesiologists not involved in the study will perform the block.

HR, mean arterial blood pressure(MAP), SpO₂, sedation score, NRS for pain will be recorded at 0h, 4h, 6h, 12 h and 24h postoperatively.

Sedation will be assessed using Modified Ramsay's sedation scale (MRSS) from 1-6 as follows:

1= anxious, agitated, restless

2= co-operative, oriented, tranquil

3= responds to command only

4= brisk response to light glabellar tap or loud noise

5 = sluggish response to light glabellar tap or loud noise

6= no response

The pain intensity will be measured regularly at intervals mentioned above by Numeric Rating Scale.

0	No Pain
1–3	Mild Pain (nagging, annoying, interfering little with activities of daily living (ADLs))
4–6	Moderate Pain (interferes significantly with ADLs)
7–10	Severe Pain (disabling; unable to perform ADLs)

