Adverse events observed in the intraoperative and postoperative period, defined as follows, will be noted.

- hypotension (20% decrease relative to baseline MAP) requiring a fluid bolus

- bradycardia (HR <50 bpm) requiring atropine
- nausea, vomiting
- pruritis
- hypoxemia ($\text{SpO}_2 < 90\%$) or
- any need for additional medication.

Blood loss will be calculated and will be replaced if more than allowable blood loss.

Pain will be assessed using NRS postoperatively. Patient will be given Injection Paracetamol 15mg/kg after the surgery and then 6 hourly in the postoperative period. Nursing staff will be directed to administer Inj. Tramadol 50mg IV slowly when NRS > 3 (rescue analgesia) and Inj. Ondansetron 4mg if the patient complains of nausea or vomiting. The time between the block and the first analgesic request will be recorded as duration of analgesia. Total dose of rescue analgesics and antiemetics (Tramadol and Ondansetron) consumed in the postoperative period will be recorded.

In the post-operative period in the ward, acceptance of the procedure and satisfaction level will be asked to the patient according to Likert scale.

Likert scale

- 1 = Strongly dissatisfied
- 2 = Dissatisfied
- 3 = Neutral
- 4 = Satisfied
- 5 = Strongly satisfied

OUTCOME MEASURES

a. Primary Outcome Measures:

Duration of analgesia

b. Secondary Outcome Measures

Total dose of rescue analgesics required in the postoperative period, numeric rating scale (NRS) for pain, Sedation score

DATA MANAGEMENT AND STATISTICAL ANALYSIS

a. Data handling

Data will be entered in Microsoft Excel 2016 and converted into Statistical package for social sciences (SPSS 11.5) for statistical analysis.

b. Coding

Alpha numerical code will be used.

c. Monitoring

Data will be entered after every day of work.

d. Statistical methods proposed

- Independent paired t test to compare the mean between two groups.
- Paired t test to compare the mean values before and after the study drug administration within the same group.
- Chi square test to compare the non-parametric variables.

Probability value will be considered significant when $p < 0.05$.

e. Calculation of the sample size

This study will consider 95% confidence interval and 80% power to estimate the sample size. For this purpose, taking into account the pre-test results, Group A mean (μ_1) = 6.6 hours, Group B mean (μ_2) = 8.6 hours and combined standard deviation (σ) = 2.27.

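### The plan does not link its three tests to the secondary outcomes: chi-square for undefined variables would waste the ordering of the sedation score, and the within-group paired t test answers no between-group objective

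*Combined protocol and SAP*

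**What the plan says.** In the Combined protocol and SAP, part d of the data management and statistical analysis section (Statistical methods proposed) has three lines and a 0.05 significance rule. The first line reads "Independent paired t test to compare the mean between two groups". The second, on change inside one arm, reads "Paired t test to compare the mean values before and after the study drug administration within the same group". The third line reads "Chi square test to compare the non-parametric variables". No outcome is named in any of them, and the variables meant in the third are not defined anywhere.

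The outcome section lists the secondary outcomes as total rescue analgesic dose, NRS and sedation score. The Secondary Objectives state the comparisons. For sedation the wording is "To compare postoperative sedation score using modified Ramsay Sedation Scale between two groups". For pain scores it is "To compare the postoperative pain scores at 0, 4, 6, 12, 24 h between two groups and use of rescue analgesics". For heart rate and blood pressure it is "To compare the haemodynamics postoperatively between two groups". For adverse outcomes it is "To compare the occurrence of any postoperative complications (bradycardia, hypotension, PONV, respiratory depression) between two groups". A further objective compares the rescue analgesic requirement between the two regimens.

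On timing, the Anaesthesia technique section places the block after surgery and the wound dressing. Of the moment when drug spread is documented it says: "This time point will be considered as zero hour for our study". Heart rate, MAP, SpO2, sedation and NRS are then scheduled at 0, 4, 6, 12 and 24 h.

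**The concern.** Two of the three lines are poor as written, not merely brief.

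The paired line tests change within an arm, while the trial asks whether the arms differ. A significant change in one arm and not in the other can easily be reported as a morphine effect, although it is not a comparison of the arms.

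The chi-square line calls variables 'non-parametric', a term that describes methods. An analyst could reasonably take it to mean ordinal scores and so apply it to sedation. Chi-square treats levels 1 to 6 as unordered labels and spreads its sensitivity over every pattern of difference, so it is weak against a plain shift towards more sedation. Sedation is a stated secondary outcome and one of the ways in which an unwanted opioid effect would show.

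Because sedation could be placed under either between-group line, the choice could also be made after both results are seen.

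**Working it through.** The plan gives no figure for any secondary outcome, so there is nothing of its own to reproduce. The first two steps compare passages. The last two use assumed inputs.

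**1. Does any objective need a within-group test?** Rescue requirement, sedation, pain scores, haemodynamics and complications are all framed as comparisons of two groups. The primary objective (duration and quality of analgesia) is not worded as a before/after change. Its outcome is the time from block to first analgesic request, which has no pre-drug value. No objective calls for the paired test.

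**2. Is there a designated 'before'?** Zero hour is the completed block, so the 0 h reading and all later ones come after the drug. The Participant Record Form has rows during surgery at 0, 10 and 30 min, which precede the block but fall under spinal anaesthesia. The adverse-event definition of hypotension uses a baseline MAP without naming a row. Candidate values exist, but none is designated.

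**3. What can two within-group p-values show?** Suppose the arms do not differ and each arm's paired test has power p. The chance that exactly one arm is significant is 2p(1-p).
- p = 0.2 or 0.8: 2 × 0.2 × 0.8 = 32%
- p = 0.3 or 0.7: 2 × 0.3 × 0.7 = 42%
- p = 0.5: 2 × 0.5 × 0.5 = 50%

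This discordant pattern is common with no morphine effect at all.

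**4. What does chi-square cost on sedation?** Inputs: 35 per arm and two-sided 0.05 (from the plan); the control distribution over levels 1-6 and the odds ratio (OR) are assumed. Under proportional odds, a control cumulative proportion c becomes c / (c + OR × (1 - c)) in the other arm. Take control 5/75/15/4/1/0% and OR 3:
- up to level 1: 0.05 / (0.05 + 3 × 0.95) = 0.017
- up to level 2: 0.80 / (0.80 + 3 × 0.20) = 0.571
- up to level 3: 0.95 / (0.95 + 3 × 0.05) = 0.864
- up to level 4: 0.99 / (0.99 + 3 × 0.01) = 0.971

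Differencing unrounded values gives about 1.7/55.4/29.2/10.7/2.9/0%. Simulated power, with uncorrected chi-square:

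| Control distribution (%) | OR | Chi-square | Mann-Whitney | t test | Chi-square loss against Mann-Whitney (points) |
|---|---|---|---|---|---|
| 5/75/15/4/1/0 | 3 | 34% | 59% | 57% | 59 - 34 = 25 |
| 5/75/15/4/1/0 | 2 | 12% | 27% | 25% | 27 - 12 = 15 |
| 3/87/8/2/0/0 | 3 | 23% | 41% | 40% | 41 - 23 = 18 |
| 3/87/8/2/0/0 | 2 | 8% | 18% | 16% | 18 - 8 = 10 |
| 10/50/25/10/4/1 | 3 | 41% | 70% | 67% | 70 - 41 = 29 |

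With 4,000 or more trials per setting, the simulation standard error is at most √(0.5 × 0.5 / 4,000) = 0.8 points. With no effect, chi-square rejects in 2-3% of trials and the other two tests in about 5%. Reporting whichever of chi-square and the t test is significant gives about 6.7% false positives for sedation in the first setting.

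**The case against.** The strongest reply is that the plan already has a between-group test of means, and that a sensible analyst would use it for everything numeric. For most outcomes this stands. Total tramadol is a dose, NRS is a 0-10 number, and heart rate and MAP are continuous; all fit the first line once 'paired' is removed from its name. A reader might infer that NRS and tramadol have no test at all. The documents do not support that. For those outcomes the defect is a wrong label and a missing list.

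A reader might also quote much larger losses, up to 48 points, for chi-square on raw NRS scores. Nothing in the plan proposes that analysis. Under the natural reading, with the t test, almost nothing is lost: even for sedation it trails Mann-Whitney by only 1-3 points. The sedation loss in the table therefore arises only if the chi-square line is followed there.

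On the paired test, it can fairly be said that pre-drug rows exist on the form. They do, and the data are not absent. What is missing is the statement of which row counts.

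The protocol also keeps allocation hidden until after analysis. That prevents choosing a test to favour a known arm, but it does not hide the p-values.

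Finally, it might be argued that Fisher's exact test should be required for rare complications. That is a trade-off. At a 10% event rate in both arms, its exact false-positive rate is 1.3%, against 5.7% for chi-square. At an assumed 3% against 20%, switching to Fisher whenever an expected count is below 5 lowers power from 68% to 49%, which makes a real harm harder to detect.

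**Conclusion.** The point holds in a limited form and should be acted on. The tests are not explicitly linked to the secondary outcomes. The between-group line is mislabelled, but is adequate for NRS, total tramadol, heart rate and MAP when read as an independent-samples t test. The chi-square line is suitable for complications and yes/no items. If followed for sedation, it costs about 10 to 29 points of power in the settings examined. Those figures rest wholly on assumed sedation distributions and odds ratios, since the documents give none.

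The paired test does not estimate the morphine effect and lacks a designated 'before' value. This conclusion rests on the text alone.

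The primary outcome is unaffected, and the point does not bear on the sample size.

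**What to change.** Replace the three lines with a short variable-to-test list:
- **NRS, total tramadol, heart rate, MAP:** independent-samples t test (correcting the label), with mean difference and 95% CI.
- **Sedation score, and satisfaction if it is analysed:** Mann-Whitney, with counts per level in each arm.
- **Complications and yes/no items:** chi-square, restricted to these. Fisher's exact test need not be required as part of this change. If a small-count method is chosen, its power cost should be stated.
- **Within-group before/after tests:** drop them, or label them descriptive, name the row used as 'before', and draw no conclusion about morphine from them.

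The cost is a few lines of rewording, with no new data, patients or procedures. For sedation, Mann-Whitney gains only 1-3 points over the t test; the benefit lies in ruling out chi-square. The list does not settle how the five reading times of NRS and sedation are to be handled, which is a separate matter.

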Intra operative complications:

- Hypotension:
- Bradycardia:
- Nausea and vomiting:
- Respiratory depression:
- Others:
- Any medication used:

Level of SAB at the time of FICB:

Time of administration of first dose of rescue analgesia:

Total duration analgesia with block:

Total dose of IV Tramadol given:

Total dose of IV Ondansetron given:

Postoperative complication (Nausea/ vomiting/ bradycardia/ hypotension/ respiratory depression:

I would like to repeat the procedure if there is a need in the future: Yes/No

Patient's satisfaction level (Likert scale- 1 = Strongly dissatisfied, 2 = Dissatisfied, 3 = Neutral, 4 = Satisfied, 5 = Strongly satisfied):

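### The record form has no postoperative prompt for pruritus or hypoxaemia and no postoperative catch-all line, and respiratory depression is compared without a criterion

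*Combined protocol and SAP*

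**What the plan says.** Four places in the combined protocol and SAP bear on this.

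- **Methods, adverse events.** The list opens with "Adverse events observed in the intraoperative and postoperative period, defined as follows, will be noted". It names hypotension and bradycardia (each with a criterion), nausea and vomiting, pruritus (by name only), hypoxaemia (SpO2 below 90%) and "any need for additional medication". Respiratory depression is not on it.
- **Secondary Objectives.** One objective is "To compare the occurrence of any postoperative complications (bradycardia, hypotension, PONV, respiratory depression) between two groups". Pruritus and hypoxaemia are not named.
- **Participant Record Form.** The postoperative line reads "Postoperative complication (Nausea/ vomiting/ bradycardia/ hypotension/ respiratory depression". The form's 'Others' and 'Any medication used' entries are both in the intraoperative block. The parameter table has columns for RR, SpO2 and sedation (MRSS), with postoperative rows at 0, 4, 8, 12 and 24 h.
- **Methods, Anaesthesia technique.** The block follows surgery: "After the completion of surgery and application dressing on the surgical wound the patient will be positioned supine". For monitoring, "HR, mean arterial blood pressure(MAP), SpO₂, sedation score, NRS for pain will be recorded at 0h, 4h, 6h, 12 h and 24h postoperatively". Respiratory rate is not in that sentence.

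**The concern.** The arms differ only in whether the 2 ml added to ropivacaine is saline or morphine 1 mg/ml. Any difference in adverse events between them is therefore read as an effect of morphine. The Methods single out pruritus as an event to note, yet the form does not ask about it in the only period when a patient could have it from the study drug. A blank line cannot tell a patient without itching from one who was never asked. Follow-up ends 24 hours after surgery, and itching not recorded in that time is hard to recover later.

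A separate weakness affects respiratory depression. It is to be compared between groups, but each recorder must decide what counts.

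**Working it through.** Nothing in the plan's own figures needs reproducing here. The check sets the lists side by side.

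| Event | Methods list | Secondary objective | Postoperative line on form | Other postoperative place on form |
|---|---|---|---|---|
| Hypotension | Yes, with criterion | Yes | Yes | MAP column |
| Bradycardia | Yes, with criterion | Yes | Yes | HR column |
| Nausea, vomiting | Yes, by name | Yes (PONV) | Yes | Ondansetron, by interval and total |
| Pruritus | Yes, by name | No | No | None |
| Hypoxaemia | Yes, SpO2 < 90% | No | No | SpO2 column |
| Respiratory depression | No | Yes | Yes, no criterion | RR and SpO2 columns |
| Sedation | No | Yes (separate objective) | No | MRSS column |

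**Pruritus.** It is the only named event in the Methods list with no postoperative entry of any kind. The intraoperative 'Others' field does not help, because it covers the period before the block.

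**Hypoxaemia.** Its defining variable is tabulated, so SpO2 < 90% can be derived at each scheduled reading. Episodes between readings have no named field. The intervals are:
- Methods times (0, 4, 6, 12, 24 h): 4, 2, 6 and 12 h.
- Form times (0, 4, 8, 12, 24 h): 4, 4, 4 and 12 h.

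The longest interval is 12 h on either schedule. The two schedules disagree (6 h against 8 h) and must be reconciled in any case.

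**Respiratory depression.** No section gives a criterion. The form collects RR and SpO2, from which one could be built, but sets no rule for using them.

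**Illustration of size for pruritus.** The documents give no pruritus rate, so the rate below is an assumption.
- Group size, from the sample-size section: 35.
- Expected cases in Group B at 10%: 0.10 × 35 = 3.5. At 20%: 0.20 × 35 = 7.
- If blank forms were reported as 0 of 35, the one-sided 95% upper limit would be 1 − 0.05^(1/35) = 0.082, or 8.2%. That lies below the whole assumed range, so the report would appear to exclude the true rate.

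No section plans a 0/35 analysis. The calculation shows only how a missing prompt could mislead if blanks were counted as absences.

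**The case against.** The strongest defence is that the Methods already instruct staff to note pruritus after surgery, and that the postoperative line is a write-in line rather than a set of tick boxes. Nothing stops a recorder from writing pruritus there. The bracket on that line is not closed in the text as read, so the printed list may be incomplete. The objective speaks of any postoperative complications, so its bracketed items may be examples, and all four of them do appear on the form. Adverse events are not among the listed primary or secondary outcome measures.

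Much of this stands. It shows that under-recording of pruritus is a risk and not a certainty. It does not supply a prompt, and events volunteered without one are captured unreliably.

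A reader might infer more: that the whole opioid-safety comparison will be under-recorded, so that the trial could find no excess of side effects because it collected none. The documents do not support that. The one study in the Review of Literature whose side effects with added perineural morphine are specified (a popliteal-catheter study in chronic limb pain) names nausea and somnolence, and both are captured here. Nor does hypoxaemia lack a place on the form, given the SpO2 column. A yes/no box would also not detect desaturation that nobody was monitoring. Finally, an undefined term does not in itself lose events. With a blinded observer, it could raise or lower counts in both arms.

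**Conclusion.** The point holds in a limited form. Postoperative pruritus is listed as an event to note but has no prompted field and no postoperative catch-all, so it may be under-recorded. Hypoxaemia is captured only at scheduled SpO2 readings, up to 12 h apart. Respiratory depression is a compared outcome without a criterion, and the likely consequence is inconsistent classification.

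The mismatch between the lists rests on the text alone and needs no assumption, except that the form is used as printed. How many events would be missed is unknown. The figure of 3.5 to 7 patients depends on an assumed rate of 10-20%, and the 8.2% limit also depends on blanks being reported as zero. Neither should be quoted as an estimate. The primary outcome, duration of analgesia, is unaffected. The change is still worth making before data are collected, because it determines what the trial can say about a listed opioid effect.

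**What to change.** 1. In the postoperative section of the Participant Record Form, add yes/no fields for pruritus and hypoxaemia (SpO2 < 90%, as the Methods already define it) and an 'Others' line.
2. Use one adverse-event list in the secondary objective, the Methods and the form.
3. State before unblinding how respiratory depression will be classified from the RR and SpO2 already on the form. The plan reveals allocation only after analysis, so this can be settled blind. Keep it as a compared outcome: putting hypoxaemia in its place would drop an event that the objective names.
4. If RR is used in that rule, name it among the recorded variables in the Methods, and reconcile the 6 h and 8 h reading times so that both places give the same schedule.

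The cost is a one-page form revision and a few words in the Methods and the objective. It needs no additional patients or procedures.
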